#### 5.5. SAFETY ANALYSIS SET

The safety analysis set will include all subjects who receive at least 1 application of IMP. The safety analysis set summaries will be based on the actual treatment received for the whole duration of the study. The rules for handling data from subjects who receive study medication from the incorrect jar during the study will be decided on a case by case basis before database

SAP Version v2.0 Page 21 of 43

Date: 16th March 2017

lock. This analysis set will be used for all safety analyses.

### 5.6. PHARMACOKINETIC (PK) ANALYSIS SET

The PK analysis set will include all subjects in the FAS who received ZPL-521 with any valid post-baseline ZPL-521 plasma concentration result, including values below the lower limit of quantification (LLOQ). The PK analysis set summaries will be based on the actual treatment received for the whole duration of the study. The rules for handling data from subjects who receive study medication from the incorrect jar during the study will be decided on a case by case basis before database lock.

#### 5.7. PROTOCOL DEVIATIONS

All protocol deviations will be reviewed and documented before database lock. Protocol deviations will be recorded by the site staff, study monitors and medical monitor reviewers. They may also be identified through programmable checks of the data.

Key protocol deviations include:

- Violations of inclusion and exclusion criteria. This includes unknown violations at enrolment and on-study violations, like taking a prohibited medication
- Poor IMP compliance
- Subject receiving the incorrect IMP

### 6. GENERAL ASPECTS FOR STATISTICAL ANALYSIS

#### 6.1. GENERAL METHODS

All statistical tests for Cohort 3 will be 1-sided at the 0.05 level of significance and accompanied by a 2-sided 90% CI. There will not be any adjustments for multiple comparisons. No statistical testing will be performed with the data from Cohorts 1 and 2.

All summaries and listings will be presented by treatment group and by cohort. For Cohorts 1 and 2, adverse events and pharmacokinetic data will be presented by treatment group and BSA treated (10%, 40% and overall) to assess whether BSA impacts this data.

Only on-treatment records will be summarised for post-baseline visits, except follow-up, unless stated otherwise. A record is considered on-treatment if it is on or before the date of last study medication plus 1 day.

Continuous variables will be summarised using the number of observations (n), mean, standard deviation (SD), 95% Confidence interval (CI) of mean, median, minimum, and maximum. Geometric mean and coefficient of variation (CV) will be included for PK parameters, where appropriate. Categorical variables will be summarised using frequencies and percentages. The number of missing values will be presented in summary tables. The missing count will not include

SAP Version v2.0 Page 22 of 43

Date: 16th March 2017

subjects who have discontinued at earlier visits.

Unless otherwise specified, the estimated mean and median for a set of values should be printed out to 1 more decimal place than the original values, and standard deviations should be printed out to 2 more decimal places than the original values. The minimum and maximum should report the same number of decimal places as the original values. The coefficient of variation will always be reported as a percentage to 1 decimal place. Percentages will be displayed with 1 decimal place; except percentages will not be presented when the count is zero and 100% will be presented as an integer.

Unless stated otherwise, baseline will be defined as the last non-missing measurement prior to administration of the first dose of IMP.

In by-visit summary tables the baseline will be summarised using all available data, but also for each visit using only the baseline data from subjects with available data at the visit; hence the mean change from baseline will equal the mean visit value – mean baseline value.

All data will be listed. Data listings will present study days in addition to dates, where study day is derived as (assessment date – first day of dosing + 1). The first day of dosing will be identified as Study Day 1.

All statistical analyses will be performed using SAS® (Version 9.2 or higher, SAS Institute Inc., Cary, NC, USA).

#### 6.2. MISSING DATA

All possible efforts will be made to ensure that subjects complete all the required assessments. As missing data may potentially bias the outcome of the statistical analyses and the subsequent estimation of the magnitude of the treatment effect, different strategies will be applied to provide a balanced assessment of treatment efficacy.

Raw data will be reported in subject listings, but where imputed data are also presented (e.g. study start and stop days) they will be identified as imputed values in the listings.

Specific approaches for handling missing data are described below. Other missing data will not be imputed.

### 6.2.1. Efficacy Data

Missing efficacy data for Cohort 3 may result from:

- subject discontinuing from the study
- for data collected at the site the assessment may have been missed

For the sensitivity analysis of the primary efficacy endpoint missing values will be imputed using Markov Chain Monte Carlo (MCMC) multiple imputation methods. Means and variances from the

SAP Version v2.0 Page 23 of 43

Date: 16th March 2017

available data will be used to determine the MCMC starting values; imputed values will be selected with maximum likelihood methods. Initially, 200 MCMC runs will be generated before selecting the first imputed data set. An additional 24 data sets will be generated, separated by 100 iterations of the MCMC. The number of data sets may be increased if the analyses are not found to be sufficiently stable with respect to standard errors and p-values. Randomisation seed numbers will be specified for the MCMC run to ensure consistency and repeatability. These imputations will be performed separately within each treatment group.

The MCMC imputation assumes that data are missing at random.

To assess the influence of missing data several sensitivity analyses will be conducted for the primary efficacy endpoint, including a last observation carried forward (LOCF) analysis and worst case imputations when the missingness is considered informative; e.g. subject withdrew due to lack of efficacy. Details regarding which approaches will be used are in Section 8.1.1.

Missing categorical data will generally be considered as a non-response when dichotomizing responses for logistic modelling. Specific details are described in Section 8.

#### 6.2.2. Pharmacokinetic Data

Concentrations of ZPL-5212372 reported as <LOQ will be taken as zero in the calculation of descriptive statistics. The data will be presented as <LOQ in the listing, with LOQ replaced by the relevant LOQ value.

For the calculation of PK parameters the following rules will apply:

- the value will be taken as zero for all values <LOQ before the first quantifiable concentration
- the value will be taken as missing for all values <LOQ after the last quantifiable concentration
- for values between quantifiable concentrations the pharmacokineticist will decide whether the value should be considered as missing or taken as zero base on the plausibility of a <LOQ value in the context of the whole concentration time profile. The pharmacokineticist will document this decision along with the justification.

Missing AUC and  $C_{max}$  values due to all concentrations recorded as <LOQ will be set to zero for the calculation of descriptive statistics, except for geometric mean where values will be treated equal to LOQ.

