## 1.5 Dose Rationale

The dose selected for this study is a 1.0% (w/w) ZPL-5212372 topical ointment, to be applied twice daily for up to 2 weeks.

The 1.0% (w/w) concentration of ZPL-5212372 has been selected to be 3 fold lower than the maximum concentration applied twice daily to mini-pigs for 14 days with no local toleration or systemic toxicity issues. Currently there is no predicted efficacious dose level for topically administered ZPL-5212372 in humans. At the present time the only human plasma exposure data for ZPL-5212372 is from the inhaled first in man (FIM) study conducted by Pfizer when ZPL-5212372 was being developed as a potential treatment for asthma. Systemic exposures of ZPL-5212372 following a single 10 mg inhaled dose resulted in an AUC0-12 1.32 ng.h/mL and Cmax 0.32 ng/mL. The human systemic exposures following topical administration are also expected to be low and this is further supported by the much lower systemic exposures seen in mini-pig following topical administration compared to the systemic exposures in rats seen following SC administration of ZPL-5212372. In addition the NOAELs in the 14 day repeat dose studies in both the rat (SC) and mini-pig (topically) were the highest dose levels administered. PK data, in addition to safety data, will be collected in the initial clinical study with topically administered ZPL-5212372, hence both systemic exposure and safety can be carefully monitored. Topical application of ZPL-5212372 to humans is expected to give low systemic exposure and plasma exposures will be monitored on an on-going basis to avoid systemic plasma exposures exceeding the mean AUC0-t value of 13550 ng.h/mL (the mean NOEL (15 mg/kg/day) systemic exposure seen in the rat after SC dosing for 13 days). Exposures in humans following a topical dose of 1.0% (w/w) ZPL-5212372 ointment are not expected to exceed the exposures seen in the mini-pig following the 30 mg/kg/day dose (mean AUC0-t 651 ng.h/mL).

Pre-clinical studies indicate that ZPL-5212372 has a low potential for drug-drug interactions as either victim or perpetrator. ZPL-5212372 is primarily hepatically cleared. ZPL-5212372 is highly bound to plasma protein, yet with very high rates of unbound clearance hence circulating systemic drug levels are low, ensuring high systemic safety from topical delivery. In addition the inhibitory effect of ZPL-5212372 has been shown to be reversible.

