**Day 1:** 

AUC $_{\tau}$  The area under the serum concentration versus time curve, from time 0 to 12

hours, as calculated using the linear trapezoidal method when concentrations are increasing and the logarithmic trapezoidal method when concentrations

Date: 16th March 2017

are decreasing.

Cmax Maximum observed drug concentration.

 $T_{max}$  Time of the maximum serum concentration. If the maximum value occurs at

more than one time point,  $T_{\text{max}}$  is defined as the first time point with this value.

Day 7:

AUC $_{\tau}$  The area under the serum concentration versus time curve, from time 0 to 12

hours, as calculated using the linear trapezoidal method when concentrations are increasing and the logarithmic trapezoidal method when concentrations

are decreasing.

AUClast The area under the serum concentration versus time curve, from time 0 to last

available time point (48 hours), as calculated using the linear trapezoidal method when concentrations are increasing and the logarithmic trapezoidal

method when concentrations are decreasing.

Cmax Maximum observed drug concentration.

Tmax Time of the maximum serum concentration. If the maximum value occurs at

more than one time point,  $T_{max}$  is defined as the first time point with this value.

Kel Where possible, the apparent terminal elimination phase rate constant (kel) will

be calculated by linear regression of the log-linear plasma concentration-time curve. Only those time points judged to describe the terminal log-linear decline will be used in the regression. Values for this parameter will only be reported for an individual if a minimum of 3 measurable concentration-time-points during the log-linear portion of the terminal elimination phase,

excluding Cmax, are available

t½ Apparent first-order terminal elimination half-life will be calculated as ln2/kel

RAUC $\tau$  Accumulation ratio calculated as Day 7 AUC $\tau$  / Day 1 AUC $\tau$ 

RCmax Accumulation ratio calculated as Day 7 Cmax / Day 1 Cmax

SAP Version v2.0 Page 20 of 43

Date: 16th March 2017

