#### 9.2. PHARMACOKINETIC PARAMETER DATA

There is insufficient data to enable PK parameters to be calculated for Cohort 1 due to the very low and sporadic systemic exposure in a small number of subjects who had study ointment applied over 40% BSA.

The PK parameters for Cohort 2 will be summarised by BSA treated and Day for the PK analysis set. Geometric mean and CV will be presented for all parameters except  $t_{1/2}$ . Due to the low sporadic exposure  $T_{max}$  will not be summarized.

All PK parameters for Cohort 2 will be listed.

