#### 12. CHANGE FROM ANALYSIS PLANNED IN PROTOCOL

The changes from the analyses specified in the protocol are:

- 1. The definition of responders for IGA score in the protocol has been further clarified and made consistent with the sponsor's previous atopic dermatitis study. The definition has changed from reduction from baseline of at least 2 points, to those subjects who achieve a score of 'Clear' or 'Almost clear', or a reduction of ≥ 2 from baseline. An additional definition of IGA success has also be defined as those subjects who achieve a score of 'Clear' or 'Almost clear'.
- 2. The protocol stated that the changes from baseline at Week 2 in NRS sleep disturbance and duration of itch will be analysed using ANCOVA, however it has been decided that it is sufficient to only summarize these endpoints by treatment group and visit. Only the NRS endpoint daily pruritus will be analysed.
- 3. The protocol stated that the Draize score for Cohort 1 would be summarised by treatment group and the change from baseline in Draize score would also be summarised using categorical shift tables. However, the safety review of Cohort 1 showed that there were very few changes in Draize score; it was therefore decided that summaries were not necessary for this endpoint and the data would only be listed.
- 4. The PK analyses described in the protocol have been modified to reflect the very low and sporadic systemic exposure observed during the safety review meetings for Cohorts 1 and 2.

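### For the geometric mean, SAP 6.2.2 sets an all-below-LOQ AUC equal to LOQ, putting a concentration in place of an area, so the Cohort 2 geometric mean AUC depends on the time unit

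*SAP*

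**What the plan says.** SAP Section 6.2.2 has two rules that matter here.

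- For individual concentrations: "Concentrations of ZPL-5212372 reported as <LOQ will be taken as zero in the calculation of descriptive statistics". LOQ is thus a limit on concentration.
- For AUC and Cmax that are missing because nothing was quantifiable, the general rule is zero: "values due to all concentrations recorded as <LOQ will be set to zero for the calculation of descriptive statistics". One statistic departs from that general rule: "except for geometric mean where values will be treated equal to LOQ". This departure covers AUC and Cmax together and has no time multiplier.

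SAP Section 4.5 defines AUCtau on Days 1 and 7 as an area: "The area under the serum concentration versus time curve, from time 0 to 12", with time in hours. The Day 7 AUClast is an area too: "The area under the serum concentration versus time curve, from time 0 to last", with 48 h as the end of the interval. Protocol Section 1.5 shows the units in use: the inhaled dose "resulted in an AUC 0-12 1.32 ng.h/mL and C max 0.32 ng/mL".

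SAP Section 9.2 applies the geometric mean to the Cohort 2 parameters, summarised by BSA treated and by day: "Geometric mean and CV will be presented for all parameters except" half-life. No other section gives a separate rule for AUC.

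**The concern.** A concentration limit cannot stand in for an area. Entering the bare LOQ figure as an AUC amounts to LOQ x 1 h if AUC is held in hours and LOQ x 1 min if it is held in minutes. The choice of time unit then changes the reported result.

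The same subjects also enter two columns of one table with different values: zero for the arithmetic statistics and LOQ for the geometric mean. On a single set of positive numbers a geometric mean cannot exceed the arithmetic mean. Here it can.

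The rule is likely to be triggered. SAP Section 12 says the PK analyses were changed to "reflect the very low and sporadic systemic exposure observed during the safety review meetings for Cohorts 1 and 2". Systemic pharmacokinetics is the secondary objective for Cohort 2, so this table is the one that reports on it.

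**Working it through.** The plan states no figure to reproduce. The check is one of units, followed by illustrations. The LOQ is not given, so AUC is written as a multiple of LOQ (LOQ.h).

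**Inputs**
- AUCtau covers 12 h and AUClast covers 48 h (SAP 4.5).
- Nominal sampling is pre-dose and 1, 2, 4, 8 and 12 h, continuing on Day 7 to 16, 24, 36 and 48 h (schedule of activities, Cohort 2).
- Planned active subjects in Cohort 2 are 6 of 9 at 40% BSA and 2 of 3 at 10% BSA (Protocol 3.1).
- The number all below LOQ, k, is not given and is varied.

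**1. Dependence on the time unit.** Moving from hours to minutes multiplies each measured AUC by 60 but leaves the substituted LOQ unchanged. After conversion back to hours, the geometric mean is lower by 60^(k/n). Assumed example: n = 6, k = 3, the other three with AUCtau = 24 LOQ.h.
- Held in hours: (24^3 x 1^3)^(1/6) = 4.90 LOQ.h.
- Held in minutes, converted back: (1440^3 x 1^3)^(1/6) / 60 = 0.63 LOQ.h.
- Ratio: 60^(3/6) = 7.75.

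**2. Geometric mean above arithmetic mean.** Assumed example: three of six all below LOQ and three with AUC = 3 LOQ.h.
- Arithmetic mean, using zeros: (3 x 3 + 3 x 0) / 6 = 1.5 LOQ.h.
- Geometric mean, using LOQ: (3^3 x 1^3)^(1/6) = 1.73 LOQ.h.

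**3. Gap between the current rule and the upper bound.** A profile held at LOQ throughout has AUCtau = 12 x LOQ and AUC over 0 to 48 h = 48 x LOQ. Replacing LOQ by these bounds multiplies the geometric mean by 12^(k/n) or 48^(k/n).

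| All below LOQ | AUCtau, 12^(k/n) | AUClast, 48^(k/n) | Hours versus minutes, 60^(k/n) |
|---|---|---|---|
| 1 of 6 | 1.51 | 1.91 | 1.98 |
| 2 of 6 | 2.29 | 3.63 | 3.91 |
| 3 of 6 | 3.46 | 6.93 | 7.75 |
| 1 of 2 | 3.46 | 6.93 | 7.75 |

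**4. Whether the upper bound could be the main substitution.** For parameter calculation, SAP 6.2.2 takes values below LOQ as zero before the first quantifiable concentration and as missing after the last. A subject with one detection C then has a triangular area of half the preceding interval times C.
- AUCtau: the longest interval is 4 h, so at most 4 x C / 2 = 2C. A detection at 4 h gives 2 x C / 2 = 1C.
- AUClast: the longest interval is 12 h, so at most 12 x C / 2 = 6C.

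An undetected subject assigned 12 x LOQ or 48 x LOQ would outrank such a subject unless C reached at least 6 x LOQ (12 / 2) or 8 x LOQ (48 / 6). The bound is therefore not suitable as the main rule.

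**The case against.** The strongest reply is that this is a slip in one descriptive statistic and hides little. SAP 6.1 also provides the mean, median, minimum and maximum, and calls for geometric means only where appropriate. Section 9.2 lists every Cohort 2 parameter, and Section 9.1 lists all concentrations and counts those below LOQ. With about 2 and 6 active subjects, a reader could find each affected case. That stands and limits the consequence, but a listing does not make the tabulated figure meaningful.

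It can also be said that the word values in the exception means concentrations, each set to LOQ and then integrated, which would give 12 x LOQ for AUCtau. The grammar points to AUC and Cmax, and no integration is described. If the other reading is possible, two programmers could differ 12-fold for each substituted subject, which is itself a reason to clarify.

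Three stronger readings are tempting, but the documents do not support them.

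- **That exposure is understated.** The true AUC of an all-below-LOQ subject lies between zero and LOQ x duration, and LOQ x 1 h is inside that range. The 12^(k/n) and 48^(k/n) factors measure distance from a ceiling, not bias.
- **That accumulation ratios become undefined through a zero Day 1 value.** Section 6.2.2 treats these parameters as missing and uses zero only in descriptive statistics. A missing Day 1 parameter gives a missing ratio.
- **That cohort progression is affected.** Protocol 3.6 and 3.7.1 compare mean AUCtau with 13550 ng.h/mL, and SAP Section 12 shows that the Cohort 1 and 2 safety reviews had already been held.

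**Conclusion.** The rule is wrong as written for AUC and sound for Cmax. For AUC it yields a geometric mean that changes by 60^(k/n) with the time unit and that can lie above the arithmetic mean in the same table.

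The size in this trial cannot be fixed. It depends on an LOQ and a count of all-below-LOQ subjects that the documents do not give, and on active numbers that are planned rather than final. For 1 to 3 of a planned 6 subjects, the gap to the upper bound is 1.5 to 3.5 for AUCtau and 1.9 to 6.9 for AUClast. That the rule will be triggered in Cohort 2 is an inference from the reported low and sporadic exposure. It is likely, not documented.

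The reach is narrow. Cohort 1 parameters are not calculated, Cohort 3 has trough concentrations only, and efficacy is untouched.

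**What to change.** Amend SAP 6.2.2, with a matching line in 9.2:

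- Keep the LOQ substitution in the geometric mean for Cmax only.
- For AUCtau and AUClast, compute the geometric mean over subjects with a calculable AUC, and print beside it the number all below LOQ. Without that count the figure would describe only the subjects with detected exposure.
- Add a sensitivity row, labelled as an upper bound, using LOQ x 12 h for AUCtau and LOQ x 48 h for AUClast.
- Leave the arithmetic statistics as they are, so that the ordering problem in step 4 is not carried into the mean, median and maximum.

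The cost is a short change to one rule and minor PK programming. SAP Section 2 allows amendments before database lock.

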### 6.2.3. Safety Data

AEs with missing classification will be assumed to be the following:

missing causality will be taken as treatment related

SAP Version v2.0 Page 24 of 43

Date: 16th March 2017

- missing seriousness will be taken as serious
- missing severity will be taken as severe

Handling of missing dates is detailed in the relevant sections below.

### 6.3. VISIT WINDOWS

There is no requirement for visit windows for Cohorts 1 and 2 as subjects will remain in the CRU for the duration of the study, so all assessments will be presented and analysed according to the visit assessment recorded.

For Cohort 3, all assessments will be presented and analysed according to the visit assessment recorded. Due to the short study duration visit windows will not be used. If possible, any early termination visits will be assigned to the closest study visit if they are on-treatment. Prior to database lock the data will be reviewed to identify any outlying visits and make decisions on how to deal with any issues. All decisions will be documented prior to database lock.

#### 6.4. STRATIFICATION

No stratification is used for the randomisation in Cohorts 1 and 2.

The randomisation for Cohort 3 is stratified by baseline EASI (≤20 or >20). This will be checked and any subjects who were misallocated to the wrong strata will be summarised according to the group they should have been assigned to. Misallocations will be listed.

### 6.5. SUBGROUPS

The following subgroups will be considered for Cohort 3 only:

Stratification subgroup: baseline EASI (≤20 or >20)

# 7. DEMOGRAPHIC, OTHER BASELINE CHARACTERISTICS AND MEDICATION

#### 7.1. PATIENT DISPOSITION AND WITHDRAWALS

The following will be tabulated over all screened subjects (the number of subjects in the screened set will be used as the denominator in the calculation of percentages):

- Number of subjects screened
- Number (%) of subjects who enter the washout period
- Number (%) of subjects who withdraw prior to the washout period
- Number (%) of subjects who withdraw prior to randomisation
- Number (%) subjects withdrawing before randomisation by reason

SAP Version v2.0 Page 25 of 43

Date: 16th March 2017

• Number (%) of subjects randomised

The following will be tabulated for each treatment group (the number of subjects in the Randomised set will be used as the denominator in the calculation of percentages):

- Number of subjects randomised
- Number (%) of subjects who complete the treatment period
- Number (%) of subjects who withdraw during the treatment period
- Number (%) subjects withdrawing during treatment period by reason
- Number (%) of subjects who complete the post-dose study follow-up
- Number (%) of subjects who withdraw between last dose of study medication and the post-dose follow-up visit.
- Number (%) subjects who withdraw during follow-up by reason

In addition the number (%) of subjects in each analysis set will also be tabulated.

